13.2. The number of participants

Given the exploratory nature of the trial, 100 patients will be recruited by group.

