4. CLINICAL INVESTIGATION SUMMARY

Title	CT Lucia 601 IOL implantation in the sulcus
Reference Number (Acronym)	CLuS
Clinical phase	Post-marketing study (phase 4)
Objectives	To perform a retrospective investigation of the CT Lucia 601 IOL implantation in the sulcus

Endpoints	Primary endpoint: determine whether the CT Lucia 601 IOL can be used safely in the sulcus
Design	Non-commercial (academic with study grant), monocentric, post-interventional observational without use of a study drug
Data Collection	A single late-postoperative visit, scheduled ≥ 6 months after the vitrectomy See Study Flow Chart 7.3
Planned Clinical investigation Period	2019-2020
Clinical investigation population	Patients who had an implantation of the CT Lucia 601 lens
Number of Participants	100
Inclusion/Exclusion Criteria	
Inclusion criteria
 
 • Patients with an implantation of a CT Lucia 601 lens for different reasons: 
 ○ During vitrectomy to treat a complicated cataract surgery and had the implantation of a CT Lucia 601 IOL in the sulcus or patients ○ During phaco surgery with a posterior capsule tear that necessitated the implantation of the implant lens in the sulcus ○ Explantation of an in-the-bag lens and implantation of a CT Lucia 601 as replacement lens (e.g. to treat opacification of the implant lens or intolerance of the implant lens). • Age : > 18 years • Signed informed consent • Preoperative myopia less than 10 diopters • Implantation of the CT Lucia IOL at least six months earlier 
Exclusion criteria
 
 • History of uveitis • Ocular pathology or history that could influence the biometry of the effective lens position, such as ocular trauma with zonulolysis, congenital iris- or lens defects etc. • Any eye condition influencing the lens position (to be specified) according to the investigator
Device Name	CT LUCIA hydrophobic C-loop IOL: CT Lucia® 601P (hydrophobic acrylic with heparin coated surface)

Principle Intended Use	All devices are CE marked and used within their claimed intended use. In general, all devices are intended to be used during ophthalmic surgery.
Manufacturer Name	CT LUCIA 601P

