8. CLINICAL INVESTIGATION POPULATION

8.1. Number of participants

A total of 100 patients will be included.

Estimated enrolment time is 12 months

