9.2. Consenting participants

Patients that had an implantation of the CT Lucia 601 at least 6 months ago, will receive a phone call of the study nurse and will receive an informed consent at home. After 2 weeks the study nurse will make a second call to ask the patients to participate in the clinical trial. Per patient, both eyes will be eligible for inclusion in the study. The contralateral eye without CT Lucia 601 will be used to create a control group.

Following the guidelines of the Ethics Review Committee of the World Health Organisation (WHO ERC), potential participant must personally sign and date the latest approved version of the informed consent form before any clinical investigations are performed.

Written and verbal versions of the participant information and Informed consent will be presented to the participants detailing no less than: the exact nature of the clinical investigation; the implications and constraints of the clinical investigation plan; the known side effects and any risks involved in taking part. It will be clearly stated that the participant is free to withdraw from the clinical investigation at any time for any reason without prejudice to future care, and with no obligation to give the reason for withdrawal.

The participant will be allowed as much time as wished to consider the information, and the opportunity to question the Investigator, their GP or other independent parties to decide whether they will participate in the clinical investigation. Written Informed Consent will then be obtained by means of participant dated signature and dated signature of the person who presented and obtained the informed consent. The person who obtained the consent must be suitably qualified and experienced, and have been authorised to do so by the Coordinating/Principal Investigator. A copy of the signed Informed Consent will be given to the participants. The original signed form will be retained at the clinical investigation site.

In case of updates of the participant information and Informed consent the participant must personally sign and date the latest approved version of the informed consent form before any further clinical investigation specific procedures are performed.

For this clinical trial, signature for approval from the patient will be obtained at the appointment in the hospital on the date agreed with the study nurse.

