13. STATISTICS

13.1. Description of statistical methods

The results from this clinical investigation will be presented with descriptive statistics. No hypothesis testing is planned for this investigation.

For continuous variables (ex: age)

In case, the data follow of a normal distribution the T-Test will be applied and the data will be reported as the means and standard deviations by group. Otherwise a signed-rank test of Wilcoxon will be performed and the data will be report as the medians and interquartile ranges.

For count data, the Pearson's Chi² test will be applied to compare the groups and the data will be reported by counts and proportions by group.

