13.3. The level of statistical significance

For all analyses, the level of significance will be 5% two-sided significant level.

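### The primary question is whether the lens is safe in the sulcus, but binary safety outcomes get no confidence interval and the 100 patients have no stated precision

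*Combined protocol and SAP*

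**What the plan says.** The endpoints row of Section 4 reads "Primary endpoint: determine whether the CT Lucia 601 IOL can be used safely in the sulcus". Section 6 lists the parameters to be collected. Some are continuous or graded, such as flare, intra-ocular pressure, visual acuity and aberrations. Others are present or absent, such as macular oedema and adverse ophthalmic events. Neither section says which findings would count against safety, or at what frequency.

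Section 8.1 sets the size: "A total of 100 patients will be included". Section 13.2 is a single sentence: "Given the exploratory nature of the trial, 100 patients will be recruited by group". It gives no expected rate, margin, power or target width.

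Section 13.1 says "No hypothesis testing is planned for this investigation", then lists tests. For count data it specifies Pearson's Chi-squared test and that "the data will be reported by counts and proportions by group". Section 13.3 adds "For all analyses, the level of significance will be 5% two-sided significant level". The comparison group is described in Section 9.2: "The contralateral eye without CT Lucia 601 will be used to create a control group". No section mentions a confidence interval.

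**The concern.** The primary endpoint asks a yes-or-no question about safety, and for uncommon complications the planned summary is a percentage and a between-group test. If few or no events are seen, the report would show 0% or 1% and nothing about how high the true frequency could still be. Section 10.1 describes use in the sulcus as off-label, so readers may give this result some weight. Without an interval they cannot tell a reassuring result from one that merely reflects a modest number of eyes.

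**Working it through.** **Inputs.** The sample size is 100 patients (Sections 8.1 and 13.2). The level is 5% two-sided (Section 13.3), which corresponds to a 95% two-sided interval. The documents give no complication rate, so the true rates used below are assumptions.

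**The plan's own figure.** The 100 cannot be reproduced, because no rate, power, margin or precision is given from which to derive it.

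**Denominator.** Section 8.1 gives 100 as a total and Section 13.2 gives it per group. If the groups are implanted and fellow eyes, both readings leave 100 patients with an implanted eye. Section 9.2 makes both eyes eligible, so some patients may contribute two implanted eyes, and those would be correlated. The figures below assume 100 independent implanted eyes.

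**Zero events.** The exact (Clopper-Pearson) two-sided 95% upper limit is 1 − 0.025^(1/n). With n = 100 this is 1 − 0.025^0.01 = 0.0362, or 3.6%. The choice of method matters little: Wilson gives 3.7%, the one-sided exact 95% limit is 1 − 0.05^0.01 = 2.95%, and the rule of three gives 3/100 = 3.0%.

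**A few events (exact two-sided 95% interval).**

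| Events | Reported | Interval |
|---|---|---|
| 0/100 | 0% | 0 to 3.6% |
| 1/100 | 1% | 0.03% to 5.4% |
| 2/100 | 2% | 0.24% to 7.0% |
| 5/100 | 5% | 1.6% to 11.3% |

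**Chance of seeing nothing**, (1 − p)^100, for assumed true rates p:

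- 1%: 0.99^100 = 0.366, about 37%
- 2%: 0.98^100 = 0.133, about 13%
- 3%: 0.97^100 = 0.048, about 4.8%

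**Does the planned test fill the gap?** Take 100 implanted and 100 fellow eyes, with the uncorrected Chi-squared statistic as Section 13.1 implies (pairing set aside).

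- 0 versus 0: one margin is zero, so the statistic cannot be computed.
- 3 versus 0: 200 × (3 × 100)² / (100 × 100 × 3 × 197) = 3.05, p about 0.08.
- 4 versus 0: 200 × (4 × 100)² / (100 × 100 × 4 × 196) = 4.08, p about 0.04.

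With no events the test says nothing, and a 3% versus 0% split would be reported as not significant. Neither result bounds the frequency in implanted eyes.

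**The case against.** The strongest reply is that the plan already limits itself. It calls the study exploratory, describes the results as descriptive and, in Section 6, gives the purpose as collecting safety parameters. It poses a question and nowhere says that an empty event table would prove safety. A reader might infer that the plan commits itself to concluding that the lens is safe; the wording is whether, not that, and no such conclusion is written down. This stands.

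It is also true that safety is not judged on proportions alone. Flare, pressure, acuity, lens position and aberrations are measured, and a fellow-eye comparison is planned. The zero-event problem concerns only the binary outcomes. The continuous measures inform safety, but they do not bound the frequency of uncommon complications.

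A reader might also infer that 3.6% is unacceptably high or that 100 is too few. The documents support neither, since they give no acceptable or expected rate. Nor is enlargement the obvious remedy. As an illustration, a zero-event upper limit of 2% would need ln(0.025)/ln(0.98) = 182.6, so 183 eyes, against the roughly 150 patients that Section 5 says had been implanted at the time of writing.

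Finally, Section 13.6 leaves the final statistical plan to be agreed before data lock, so intervals could be added there. That gives an opportunity and not a commitment, and the endpoint wording in Section 4 belongs to the protocol itself.

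**Conclusion.** The point holds as a mismatch between the primary question and the planned summary of binary safety outcomes. As written, a low count would be offered on the question of safety with no measure of uncertainty, and the Chi-squared test does not supply one. With 100 independent implanted eyes, no events remains compatible at the two-sided 95% level with a rate of up to 3.6%, and a 1% complication is missed altogether with probability 37%.

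These figures rest on independence and on participants being representative of implanted patients. They cover sampling error only. They do not allow for patients who decline to attend, or for events that resolved before the single visit at six months or later. It would therefore be too strong to say that complications commoner than 3.6% are excluded: that needs zero events and both assumptions. The defect is not that 3.6% is too large, but that the plan gives no basis for judging safety from a count. It is a cheap improvement that changes what the study can properly conclude.

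**What to change.** - **Section 13.1:** report each binary safety outcome in implanted eyes with an exact (Clopper-Pearson) 95% confidence interval. Use one implanted eye per patient or a patient-level denominator; if both implanted eyes of a patient are counted, use an interval adjusted for clustering.
- **Section 13.2:** replace the present rationale with the expected precision at 100 patients, for example a two-sided exact 95% upper limit of 3.6% for no events and a 37% chance of seeing no case of a 1% complication. Label both as assuming independence.
- **Section 4:** reword the primary endpoint as estimating the frequency of safety events listed in advance. Limit the conclusion to the upper confidence limits observed, and note that the interval does not cover non-response or events resolved before the visit.

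The cost is wording in three sections and one extra table column. Sample size and data collection are unchanged. The downside is that the safety statement becomes less favourable.

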13.3. The level of statistical significance

For all analyses, the level of significance will be 5% two-sided significant level.

13.4. Criteria for the termination of the clinical investigation

There will be only one postoperative visit to examine the patients, the clinical investigation will be terminated after this visit. No statistical interim analysis is planned.

13.5. Procedure for accounting for missing, unused and spurious data

Missing data will be reported with reasons given where available, and the missing data pattern will be examined. We will explore the mechanism of missing data by means of logistic regression models which will explore if missingness (i.e. whether the primary outcome is missing or not) is related to measured baseline variables. Covariates found to be predictive of missingness will, where appropriate, be included as a covariate in the analysis model.

13.6. Procedures for reporting any deviations from the original statistical plan

The final statistical plan will be agreed prior to final data lock and prior to any analyses taking place. Any deviation thereafter will be reported in the final trial report.

13.7. Inclusion in analysis

All patients who received a CT Lucia 601P IOL will be contacted and asked to participate in the trial.

14. Clinical Investigation Management

14.2. Clinical investigation steering committee

Patients included in this clinical trial follow the standard clinical path, underwent prior surgery using the standard vitrectomy device and using the currently used instruments. During the (single) study visit, all tests are non-contact examinations and performed by an experienced study nurse. Hence, there is no increased safety risk for patients enrolled in this investigation. For this this reason, no steering committee or DMC will be constituted.

14.3. Data monitoring committee

N/A, see section 14.2.

14.4. Monitoring plan

The study protocol will be reviewed by the CTC prior to study approval. If the CTC evaluates that the study should be monitored, a monitor will be appointed by the CTC. In this case, the monitor will visit the Investigator site prior to the start of the clinical investigation and during the course of the clinical investigation if required, in accordance with the monitoring plan. Monitoring will be performed according to ISO 14155:2011.

Data will be evaluated for compliance with the clinical investigation plan and accuracy in relation to source documents. Following written standard operating procedures, the monitors will verify that the clinical investigation is conducted and data are generated, documented and reported in compliance with the clinical investigation plan, GCP and the applicable regulatory requirements.

15. GOOD CLINICAL PRACTICE

15.1. Declaration of Helsinki

The Investigator will ensure that this clinical investigation is conducted in full conformity with the current revision of the Declaration of Helsinki (last amended October 2000, with additional footnotes added 2002 and 2004).

15.2. Guidelines for GCP

The Investigator will ensure that this clinical investigation is conducted in full conformity with relevant regulations and with the International standard for Good Clinical Practice for clinical investigations of medical devices for human subjects (ISO 14155:2011).

15.3. Ethics review

The clinical investigation plan, Investigator's Brochure, Case Report Forms (CRFs), informed consent form, participant information sheet and any other documents needed for review by an appropriate Ethics Committee (EC) or regulatory authority will be submitted to obtain written approval. Any additional requirements imposed by the EC or regulatory authority will be followed, if appropriate.

The Investigator will submit and, where necessary, obtain approval for all amendments to the original approved documents. Furthermore, the clinical investigation will not begin until the required approval/favourable opinion of the EC or regulatory authority has been obtained.

15.4. Patient Information and Consent Form

The Principal Investigator will ensure that the subject is given full and adequate oral and written information about the nature, purpose, possible risks and benefits of the investigation. Subjects must also be notified that they are free to discontinue participation in the investigation at any time. The subject should be given the opportunity to ask questions and time for consideration.

The subject's signed informed consent has to be obtained before conducting any investigation related procedures. The original must be filed by the Principal Investigator. A copy of the Patient Information including the signed Consent Form should be given to the subject. If modifications are made according to local requirements, the new version must be approved by the EC.

15.5. Subject data protection

The clinical investigation staff shall treat all information and data relating to the Study disclosed to Participating Site and/or Investigator in this Study as confidential and shall not disclose such information to any third parties or use such information for any purpose other than the performance of the Study. The collection, processing and disclosure of personal data, such as patient health and medical information is subject to compliance with applicable personal data protection and the processing of personal data (Regulation (EU) 2016/679 also referred as the General Data Protection Regulation ("GDPR") and the Belgian Law of July 30 2018 on the protection of natural persons with regard to the processing of personal data)

The clinical investigation staff will ensure that the participants' anonymity is maintained. The participants will be identified only by initials and a participants ID number on the CRF and any electronic database. All documents will be stored securely and only accessible by clinical investigation staff and authorised personnel. The clinical investigation will comply

with the Data Protection Act which requires data to be anonymised as soon as it is practical to do so.

15.6. Procedures in case of medical emergency

The Principal Investigator is responsible for ensuring that procedures and expertise are available to cope with medical emergencies during the investigation.

16. CLINICAL INVESTIGATION CONDUCT RESPONSIBILITIES

16.1. Clinical investigation plan amendments

Amendments to the clinical investigation plan must be submitted to the Sponsor for review before submitting to the appropriate EC and Regulatory Authority for approval.

16.2. Clinical investigation plan violations, deviations and serious breaches

The Clinical investigator will not implement any deviation from the clinical investigation plan without agreement from the Sponsor, except where necessary to eliminate an immediate hazard to clinical investigation participants.

In the event that the Clinical investigator needs to deviate from the clinical investigation plan, the nature of and reasons for the deviation will be recorded in the CRF and notified to the Sponsor. If this necessitates a subsequent clinical investigation plan amendment, this will be submitted to the Sponsor for approval and then to the appropriate REC and Regulatory Authority for review and approvals as appropriate. It is Sponsor policy that waivers to the clinical investigation plan will not be approved.

In the event that a serious breach of GCP is suspected, this will be reported to the Sponsor immediately.

16.3. End of clinical investigation

The end of clinical investigation is defined as the last participant's last visit.

The investigator and/or the clinical investigation steering committee have the right at any time to terminate the clinical investigation for clinical or administrative reasons.

The end of the clinical investigation will be reported to the EC and Regulatory Authority within 90 days, or 15 days if the clinical investigation is terminated prematurely. The Investigators will inform participants of the premature clinical investigation closure and ensure that the appropriate follow up is arranged for all participants involved.

A summary report of the clinical investigation will be provided to the EC and Regulatory Authority within 1 year of the end of the clinical investigation.

16.4. Insurance and indemnity

In accordance with the Belgian Law relating to experiments on human persons dated May 7, 2004, Sponsor shall assume, even without fault, the responsibility of any damages incurred by a Study Patient and linked directly or indirectly to the participation to the Study, and shall provide compensation therefore through its insurance."

16.5. Funding

A grant request to support this retrospective clinical trial will be sent to Carl Zeiss.

17. REPORTING, PUBLICATIONS AND NOTIFICATIONS OF RESULTS

17.1. Authorship policy

Ownership of the data arising from this clinical investigation resides with the clinical investigation team. On completion of the clinical investigation, the clinical investigation

data will be analysed and tabulated, and a clinical investigation report will be prepared in accordance with ISO14155:2011.

17.2. Publication

The Principal Investigator will decide to publish the obtained study data. The statistician will provide a study report, which will be used as source data to write the results section of the manuscript. The publication will also cover authorship, acknowledgements (mentioning the grant provider of the trial), and an overview of relevant scientific publications.

Before submitting for publication, the manuscript will be sent to the grant provider, allowing the grant provider give feedback on the manuscript within 2 weeks. It is up to the Principal Investigator to decide to make any changes to the manuscript based on this feedback.

19. SAFETY REPORTING

19.1. Definitions

Device Deficiency (DD)

Inadequacy of a medical device with respect to its identity, quality, durability, reliability, safety or performance.

Note:

- Device Deficiencies include malfunctions, use errors, and inadequate labelling.

All Device Deficiencies that might have led to a Serious Adverse Device Effect shall be reported in accordance with Serious Adverse Event reporting procedures, as specified below.

Adverse Event (AE)

Any untoward medical occurrence, unintended disease or injury, or any untoward clinical signs (including abnormal laboratory findings) in subjects, users or other persons, whether or not related to the investigational device.

Note:

- This definition includes events related to the investigational device or the comparator.
- This definition includes events related to the procedures involved.
- For users or other persons, this definition is restricted to events related to investigational devices.

Adverse Device Effect (ADE)

Adverse Event related to the use of an investigational device.

Note:

- This definition includes adverse events resulting from insufficient or inadequate instructions for use, deployment, implantation, or operation, or any malfunction of the investigational device.
- This definition includes any event resulting from use error or from intentional misuse of the investigational device.

Serious Adverse Event (SAE)

Adverse Event that led to any of the following:

- a) death,
- b) serious deterioration in the health of the subject, that resulted in any of the following:
 - 1) a life-threatening illness or injury,
 - 2) permanent impairment of a body structure or a body function,
 - 3) hospitalization or prolongation of patient hospitalization,
 - 4) medical or surgical intervention to prevent life-threatening illness or injury or permanent impairment to a body structure or a body function.
 - 5) chronic disease
- c) foetal distress, foetal death or a congenital physical or mental impairment or birth defect.

Note:

Planned hospitalization for a pre-existing condition, or a procedure required by the CIP, without serious deterioration in health, is not considered a serious adverse event.

Serious Adverse Device Effect (SADE)

Adverse Device Effect that has resulted in any of the consequences characteristic of a Serious Adverse Event.

19.2. Procedures for reporting SAE /SADE or DD that could have led to a SADE

All SAEs/SADEs that occurs during the Clinical Investigation shall be reported, whether or not they are considered causally related to the investigational device.

Device Deficiencies that might have led to SADE must be reported as a SADE if either

- a) suitable action had not been taken,
- b) if intervention had not been made, or
- c) if circumstances had been less fortunate

The investigator is responsible for informing the EC/IRB and/or the Competent Authority of the SAE/SADE as per local requirements. For this reason, medical device incidents will be routinely collected and reported under the national materiovigilance rules at the discretion of the Investigator.

